2.3 Exploratory Objectives

- 2.3.1 Explore the response to therapy based on CDK4, CDK6, Cyclin D1, CDKN2A and HPV genetic status.
- 2.3.2 Evaluate whether molecular and biochemical markers are predictive of tumor response.
 - 2.3.2.1 Correlate genetic subtype with response via targeted DNA and RNA-sequencing of pre-treatment biopsy.
 - 2.3.2.2 Assess the expression of CDK4, CDK6, Cyclin D1, CDKN2A in tumors as well as level of vascularization (CD31+ cells), apoptosis (TUNEL), proliferation (Ki67), and tumor infiltrating lymphocyte content (CD4/CD8, etc.).
- 2.3.3 Assess whether the dynamics of circulating tumor DNA (ctDNA) are associated with clinical and radiographic responses to therapy as well as monitor for the presence and quantity of HPV DNA or DNA containing somatic mutations identified in the targeted sequencing of the biopsy specimen.

2.4 Endpoints

2.3.1 Primary Endpoint

- 2.3.1.1 Disease control rate will be defined as the proportion of patients achieving either complete response (CR), partial response (PR), or stable disease (SD) at 12 weeks. Response will be assessed via RECIST v1.1.

2.3.2 Secondary Endpoints

- 2.3.2.1 Adverse events will be evaluated by clinical evaluation as well as routine lab work. Toxicities will be assessed via CTCAE v 4.03.

2.3.2.2 Survival endpoints to be assessed will include both overall survival and progression free survival time

3.0 PATIENT ELIGIBILITY

Subjects must meet all of the inclusion and exclusion criteria to be enrolled to the study. Study treatment may not begin until a subject is enrolled.

3.1 Inclusion Criteria

- 3.1.1 Histologically documented progressive squamous cell head and neck cancer with or without metastases, not amenable to curative treatment; or the patient has documented refusal of curative treatment.
- 3.1.2 ECOG performance status of 0-2
- 3.1.3 Presence of measurable disease by CT scan per RECIST v1.1.
- 3.1.4 Age ≥ 18 years.
- 3.1.5 Life expectancy of ≥ 12 weeks.
- 3.1.6 Women of childbearing potential must have a negative serum or urine pregnancy test at time of screening and confirmed within 3 days prior to treatment. Women not of child-bearing potential will be defined as all women older than age 50 and anovulatory for 12 months.
- 3.1.7 Signed and dated informed consent document indicating that the patient (or legally acceptable representative) has been informed of all pertinent aspects of the trial prior to enrollment.
- 3.1.8 Willingness and ability to comply with scheduled visits, treatment plans, laboratory tests, and other study procedures.

3.1.9 Adequate organ and marrow function as defined below:

WBC	$\geq 3 \times 10^9$ cells/mL
ANC	$\geq 1.5 \times 10^9$ cells/mL
Hemoglobin	≥ 9 g/dL
Platelets	$\geq 75,000$ cells/mm ³
Total Serum Bilirubin	Within 1.5 x upper limit of normal (ULN)
AST	Within 2.5 x ULN unless there are liver metastases in which case, AST within 5 x ULN
ALT	Within 2.5 x ULN unless there are liver metastases in which case, ALT within 5 x ULN
Serum Creatinine Clearance	≥ 30 mL/min

3.2 Exclusion Criteria

- 3.2.1 Previous treatment with cytotoxic chemotherapy therapy in the recurrent/metastatic setting. Previous treatment with non-cytotoxic agents and/or concurrent chemoradiation in the recurrent/metastatic setting is permitted.

- 3.2.2 Gastrointestinal abnormalities causing impaired absorption precluding administration of medications by mouth or feeding tube.
- 3.2.3 Evidence of untreated or progressive brain metastases, spinal cord compression, or carcinomatous meningitis.
- 3.2.4 A serious uncontrolled medical disorder or active infection that would impair their ability to receive study treatment.
- 3.2.5 Dementia or significantly altered mental status that would prohibit the understanding or rendering of informed consent and compliance with the requirements of this protocol.
- 3.2.6 Patients (male and female) having procreative potential who are not willing or not able to use 2 adequate methods of contraception during the study and for 90 days following their last dose of treatment. Adequate contraception is defined as:
 - a. Total abstinence or
 - b. Male or female sterilization or
 - c. Combination of any two of the following (i+ii or i+iii, or ii+iii):
 - i. Use of oral, injected or implanted hormonal methods of contraception
 - ii. Placement of an intrauterine device (IUD) or intrauterine system (IUS)
 - iii. Barrier methods of contraception: condom or occlusive cap (diaphragm or cervical/vault caps) with spermicidal foam/gel/film/cream/vaginal suppository
- 3.2.7 Women who are pregnant or breast-feeding.
- 3.2.8 Patients residing in prison.
- 3.2.9 Prior experimental therapy within 30 days of enrollment.
- 3.2.10 Availability of curative treatment option for the patient's cancer, whether surgery, chemotherapy, radiation, or combination thereof, unless the patient has documented refusal of curative treatment.
- 3.2.11 Patients with a history of severe allergic reaction to cisplatin or carboplatin

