- Palbociclib is a novel therapeutic in R/M HNSCC. Only one small phase I trial utilizing a doublet of palbociclib and cetuximab (an IgG1 anti-EGFR monoclonal antibody) has been conducted in R/M HNSCC. This phase 1 study, presented at ASCO 2015, demonstrated suggestion of activity in both p16 negative and positive patients¹⁸. Nine patients were enrolled in this Phase 1 study; 5 of whom were both platinum and cetuximab resistant, 1 of whom was cetuximab resistant. Of the nine patients, 5 patients were p16- and 4 p16+. No dose limiting toxicities or AE related treatment discontinuations were encountered hence the maximum tolerated dose (MTD) was not reached. Tumor assessment after cycle 2 demonstrated partial response (PR) in 2 patients, stable disease (SD) in 5 patients, progressive disease (PD) in 1 patient, and one patient was non-evaluable. Responses were seen in patients who were cetuximab resistant as well as those resistant to platinum and cetuximab. Based on the results of this trial, a Phase II utilizing cetuximab with palbociclib in HPV- patients is ongoing (NCT02101034). Therefore, the early results of this trial support further exploration of palbociclib in R/M HNSCC.

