1.4 Rationale in Head and Neck Cancer

Given the molecular alterations (CDKN2A, CCND1) seen in R/M HNSCC and signal of efficacy with the use of palbociclib in patients in other malignancies with these alterations, exploration in R/M HNSCC is warranted. Based on preclinical evidence, the combination of a CDK 4/6 inhibitor with cytotoxic chemotherapy in the first line setting is a rational therapeutic approach and holds promise as an effective doublet in head and neck cancer.

We propose a phase II trial to evaluate the combination of palbociclib and carboplatin for the first-line cytotoxic treatment of R/M HNSCC. This will be a single arm, non-randomized, non-blinded phase II trial. Patients with unresectable recurrent or metastatic HNSCC with no previous cytotoxic chemotherapy therapy in the recurrent/metastatic setting will be included. Previous treatment with immunotherapeutics in the recurrent/metastatic setting will be permitted.

Based on pre-clinical data, we hypothesize that this doublet will have activity in eliciting a greater antitumor response and hence improved disease control rate. Much of the benefit seen in previous palbociclib trials was SD and clinical benefit (CR + PR + SD at 24 weeks) rather than improvement in ORR, CR, or PR. As the increase in SD was associated with improved PFS compared to placebo in these trials, we believe this represents drug effect rather than disease biology. Therefore, we believe disease control rate (DCR) at 12 weeks is an appropriate primary end point for this phase II trial.

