7.1.1 Definitions

Evaluable for toxicity. All patients will be evaluable for toxicity from the time of their first treatment with study drug.

7.1.2 Evaluable for response. Only those patients who have measurable disease present at baseline and have at least one dose of each drug will be considered evaluable for response. These patients will have their response classified according to the definitions stated below. In the case of death or disease progression before response classification, the outcome will be considered PD for calculation of disease control rate. Disease Parameters

Measurable disease. Measurable lesions are defined as those that can be accurately measured in at least one dimension (longest diameter in the plane of measurement is to be recorded) with a minimum size of:

- 10mm by CT scan (irrespective of scanner type) for studies with a slice thickness of ≤ 5 mm or twice the slice thickness or MRI
- 10mm caliper measurement by clinical exam (lesions which cannot be accurately measured with calipers should be recorded as non-measurable)
- 20mm by chest X-ray (if clearly defined and surrounded by aerated lung)

All tumor measurements must be recorded in millimeters (or decimal fractions of centimeters).

Malignant lymph nodes: To be considered pathologically enlarged and measurable, a lymph node must be ≥ 15 mm in short axis when assessed by CT scan (CT scan slice thickness recommended to be no greater than 5 mm). At baseline and in follow-up, only the short axis will be measured and followed.

Tumor lesions in previously irradiated areas are considered measurable if there has been progression in the lesion since completion of radiotherapy

Non-measurable disease. All other lesions (or sites of disease), including small lesions (longest diameter < 20 mm with conventional techniques or < 10 mm using CT scan), are considered non-measurable disease. Bone lesions, leptomeningeal disease, ascites, pleural/pericardial effusions, lymphangitis cutis/pulmonis, inflammatory breast disease, abdominal masses (not followed by CT or MRI), and cystic lesions are all non-measurable.

Target lesions. All measurable lesions up to a maximum of 2 lesions per organ and 5 lesions in total should be identified as **target lesions** and recorded and measured at baseline. Target lesions should be selected on the basis of their size (lesions with the longest diameter), be representative of all involved organ,

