11.0 STATISTICAL CONSIDERATIONS

11.1 Study Design/Study Endpoints

This is an open-label multi-institution single arm Phase II study with a two-stage design. We will power this study to detect a 20% improvement in disease control rate (DCR) with the addition of palbociclib. Based on historical data, the DCR in R/M HNSCC with single agent platinum therapy is 40%^{4,64}. We hypothesize that addition of Palbociclib to carboplatin will increase the DCR at 12 weeks to 60%. We anticipate no loss to followup for this endpoint. The primary clinical objective of this trial is to estimate disease control rate (DCR) at 12 weeks in patients with metastatic head and neck squamous cell cancer treated with carboplatin and palbociclib. Response will be assessed after every two cycles. DCR will be defined as either CR, PR or SD at 12 weeks. The regimen will be considered promising if the true disease control rate is 60% or better. Conversely, if the DCR is 40% or lower, there would be little interest in pursuing this therapy in further studies. In this case, we would like to terminate the trial early and consider a new therapy. The optimal two-stage accrual design has been adopted⁶⁵.

In the first stage, we will accrue 18 response-evaluable patients as defined in section 7.1.1. If 8 or less subjects are considered DCR at 12 weeks, the trial will be stopped and we will conclude that the therapy is ineffective. If we observe 9 or more with disease control (CR, PR, or SD) at 12 weeks, trial will continue to the second stage and an additional 22 response-evaluable patients will be entered. Based on all 40 subjects, if 21 or more patients have achieved disease control, the therapy will be considered promising. If fewer than 21 evaluable subjects achieve DCR at 12 weeks, we will consider the therapy to be ineffective.

Early termination or modification for toxicity

At the initial stage, after 10 patients have been evaluated, if more than 70% experienced grade 3 or 4 toxicity events, the trial will be halted for further safety review and the investigators will consider terminating the study or adjusting the doses. Throughout the study if more than 70% of patient's experience grade 4 toxicity, then the study will be halted for consideration of further adjustments to dosing.

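### Exclusion 3.2.1 admits patients who have already progressed on palbociclib or another CDK4/6 inhibitor, and they would count in a DCR meant to show what adding palbociclib achieves; a minor gap that one line closes

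*Combined protocol and SAP*

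**What the plan says.** **Eligibility.** Section 3.2.1, repeated in the synopsis, excludes earlier cytotoxic chemotherapy in the recurrent/metastatic (R/M) setting and continues: "Previous treatment with non-cytotoxic agents and/or concurrent chemoradiation in the recurrent/metastatic setting is permitted". The only other washout or bar on earlier drug therapy for the disease is 3.2.9, "Prior experimental therapy within 30 days of enrollment", which delays entry but does not prevent it. Nothing in 3.1.1–3.1.9 or 3.2.1–3.2.11 mentions earlier palbociclib or any other CDK4/6 inhibitor.

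**Rationale.** Section 1.4 describes the intended population and says: "Previous treatment with immunotherapeutics in the recurrent/metastatic setting will be permitted".

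**Earlier use of palbociclib in this disease.** Section 1.2 reports a nine-patient phase I trial of palbociclib with cetuximab in R/M head and neck cancer and adds that "a Phase II utilizing cetuximab with palbociclib in HPV- patients is ongoing".

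**Analysis set.** Under Section 7.1, patients who have measurable disease at baseline and "have at least one dose of each drug will be considered evaluable for response". Earlier therapy plays no part in that definition.

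**Hypothesis.** Section 11.1 takes as its null that "the DCR in R/M HNSCC with single agent platinum therapy is 40" per cent, and powers the trial for a rise to 60% through the addition of palbociclib.

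**The concern.** The trial asks whether adding palbociclib to carboplatin lifts the 12-week DCR from 40% to 60%. A patient whose cancer has already progressed on a CDK4/6 inhibitor is a doubtful place to look for that gain. Section 3.2.1 is not merely silent on this: it grants a general permission for non-cytotoxic agents. Section 9.2 classes palbociclib as a CDK4/6 inhibitor, while Section 9.1 classes carboplatin as cytotoxic, so palbociclib falls on the permitted side. A registrar applying the criteria as written would have no ground to refuse such a patient.

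There is one arm and a fixed historical rate, so no concurrent control would carry the same mix of patients. If pre-exposed patients do less well, the observed DCR is diluted. What is at stake is a lower chance of recognising an active regimen, either at the 8-versus-9 of 18 decision or at the 20-versus-21 of 40 decision. Section 11.3 plans no analysis by earlier CDK4/6 inhibitor exposure that would reveal this.

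**Working it through.** **Step 1: can such a patient enter and be counted?**

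- Palbociclib with cetuximab (Section 1.2) contains no cytotoxic drug. A patient who progressed on it and had no cytotoxic chemotherapy in the R/M setting passes 3.2.1.
- If that treatment was experimental, 3.2.9 requires 30 days to have passed, after which it no longer applies.
- With measurable disease and one dose of each study drug, the patient is response-evaluable under Section 7.1 and counts in the DCR of Section 11.1.

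**Step 2: reproduce the stated design.** Inputs from Sections 11.1 and 11.2: stage 1 has 18 patients, stop at 8 or fewer with disease control; stage 2 adds 22; success is 21 or more of 40; null 0.40, target 0.60. The probability of success at a true rate p is

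P(success) = Σ over x = 9 to 18 of P[Bin(18, p) = x] × P[Bin(22, p) ≥ 21 − x], the second factor being 1 where 21 − x ≤ 0.

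- p = 0.40 gives 0.0593 (stated type I error 0.059).
- p = 0.60 gives 0.8001 (stated power 0.80).
- The chance of stopping at stage 1, P[Bin(18, p) ≤ 8], is 0.737 at p = 0.40 and 0.135 at p = 0.60.

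The design figures are reproduced.

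**Step 3: effect of pre-exposed patients.** The documents give neither their number nor their DCR, so both are assumptions. Suppose k of 40 are pre-exposed, that they do as platinum alone is assumed to do (40%), and that everyone else is at 60%. The average rate is

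p = 0.60 × (1 − k/40) + 0.40 × (k/40) = 0.60 − 0.20 × k/40.

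| k of 40 | Share | p | Power | Loss from 0.8001 | Stage 1 stop |
|---|---|---|---|---|---|
| 0 | 0% | 0.600 | 0.8001 | – | 0.135 |
| 1 | 2.5% | 0.595 | 0.7837 | 0.0164 | 0.145 |
| 2 | 5% | 0.590 | 0.7664 | 0.0337 | 0.155 |
| 4 | 10% | 0.580 | 0.7295 | 0.0706 | 0.177 |

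This applies the average rate to every patient, as if exposure were independent from patient to patient with probability k/40.

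**Step 4: effect on type I error.** Under the null the other patients are also at 40%, so p = 0.40 × (1 − k/40) + 0.40 × (k/40) = 0.40 for every k, and type I error stays at 0.0593. If pre-exposed patients did worse than 40%, p would lie below 0.40 and the false-positive rate would fall, not rise.

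**Step 5: effect of the fix on the design.** Excluding these patients changes none of the inputs in step 2, so the sample size, boundaries, type I error and power stay as they are.

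**The case against.** The strongest reply is that the effect may be nil. The documents do not give the sites, entry rules or enrolment of the ongoing palbociclib–cetuximab trial, and this trial has at most three sites. Of the nine phase I patients, five were resistant to both platinum and cetuximab, and any of them given platinum as R/M cytotoxic chemotherapy is already barred by 3.2.1. Nothing shows that even one eligible pre-exposed patient would present. This stands, and it is why the point is minor.

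Four stronger readings are tempting, and the documents do not support them.

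- *That palbociclib has already failed in these patients, so they cannot gain from it.* The rationale in Section 1.3.2 is synergy with platinum. In one cell line the survival fraction was 88% on palbociclib alone, 71% on cisplatin alone and 33% on both. That does not establish benefit after progression on a CDK4/6 inhibitor, but it rules out treating the absence of benefit as a fact.
- *That power could fall much further.* A DCR of 20% in 4 pre-exposed patients of 40 would give 0.648, but the documents offer no reason why they should do worse than the 40% assumed for platinum alone.
- *That Section 1.4 restricts earlier therapy to immunotherapeutics, so that 3.2.1 contradicts it.* Section 1.4 says that these are permitted, not that only these are. It also omits the concurrent chemoradiation that 3.2.1 allows, so it is not a complete list.
- *That the biomarker work is confounded.* The screening biopsy must be taken after any systemic therapy, so it describes the tumour actually treated. In a pre-exposed patient it could still mix acquired change with original genotype, but those aims are exploratory.

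It can also be said that medical history is taken at screening and eligibility documents are reviewed centrally, so exposure could be identified without changing a criterion. That is true, but neither step gives a reason to refuse entry, and no analysis by exposure is planned.

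**Conclusion.** The gap is real on the text. Section 3.2.1 permits any earlier non-cytotoxic agent, no other criterion bars a CDK4/6 inhibitor, and patients so treated would count in the primary endpoint. Its size is unknown and probably small. On the assumption of a 40% DCR in pre-exposed patients and 60% in the rest, one such patient in 40 costs about 1.6 points of power, two about 3.4 and four about 7.1; if none enrols, the loss is zero.

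A reader might infer that a positive result would be in doubt. It would not on this account: the bias works against the regimen and leaves type I error uninflated, so a positive finding would stand. A negative or borderline finding would be harder to interpret if such patients had enrolled. Severity is minor; the change is worth making because it costs almost nothing.

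**What to change.** - Add an exclusion to Section 3.2 and to the synopsis: *Prior treatment with palbociclib or any other CDK4/6 inhibitor.*
- In 3.2.1 and its synopsis counterpart, limit the permission to *non-cytotoxic agents other than CDK4/6 inhibitors*.
- Add the matching item to the Eligibility Worksheet.
- If the sponsor prefers to keep such patients, say so in the protocol, record earlier CDK4/6 inhibitor exposure at screening, and add to Section 11.3 a report of the 12-week DCR with and without them.

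The cost is an eligibility amendment, one worksheet item and a very small loss of candidates. The statistical design is untouched.

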4.0 SUBJECT SCREENING AND REGISTRATION PROCEDURES

Patient registration for this trial will be centrally managed by the Coordinating Center of The University of Michigan Rogel Cancer Center as described below:

A potential study subject who has been screened for the trial and who has signed the Informed Consent document will be initially documented by the participating site on the Screening and Enrollment Log provided by the Coordinating Center.

It is the responsibility of the local site investigator to determine patient eligibility prior to submitting patient registration request to the Coordinating Center. After patient eligibility has been determined, a copy of the completed Eligibility Worksheet together with all the pertinent de-identified source documents will be submitted by the requesting site to the Coordinating Center, by email to [contact].

The Multi-Site Coordinator, who acts as the registrar, will review the submitted documents and process the registration. Sites should inform the Multi-Site Coordinator of a potential registration by 5 p.m. on the day prior to registration. Same day registrations cannot be guaranteed.

An email will be sent by the registrar to the requesting site registrar to confirm patient registration and to provide the study identification number that has been assigned to the patient. In addition, a copy of the Eligibility Worksheet signed and dated by the registrar, will be sent back to the requesting site registrar.

Patients found to be ineligible for participation after being consented will be considered screen failures, and documented as such in the Screening and Enrollment Log. These patients will not have study identification number assigned to them, and will not receive study treatment.

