5.0 TREATMENT PLAN

5.1 Treatment Dosage and Administration

Protocol treatment must start within 5 business days of enrollment to the study.

5.1.1 This study will be a non-randomized phase II trial. We will enroll 40 patients with R/M HNSCC. Patients will be treated with Carboplatin (AUC=5, IV, day 1) as well as Palbociclib (125 mg, daily, days 1-14). Cycle length will be 21 days. Patients will be monitored closely for toxicity and undergo imaging to evaluate efficacy once every 2 cycles. After 6 cycles of Carboplatin + Palbociclib, if patients continue to garner a response to therapy, they will be transitioned to maintenance single agent palbociclib at a dose of 125 mg daily, days 1-21, cycle length: 28 days

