8.1.1 Contraindications

8.1.1.1 Carboplatin is contraindicated in patients with a history of severe allergic reactions to cisplatin or other platinum containing compounds

8.1.1.2 Carboplatin should not be employed in patients with severe bone marrow depression or significant bleeding

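### Exclusion 3.2.11 is narrower than the protocol's own carboplatin contraindication: severe allergy to a platinum drug other than cisplatin or carboplatin does not bar enrolment

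*Combined protocol and SAP*

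**What the plan says.** Section 3.0 makes Section 3 the enrolment rule: "Subjects must meet all of the inclusion and exclusion criteria to be enrolled to the study". The only criterion there on drug allergy is 3.2.11, which excludes "Patients with a history of severe allergic reaction to cisplatin or carboplatin". Item 11 of the synopsis exclusion list has the same wording.

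Section 8.1.1.1, under the carboplatin contraindications, states: "Carboplatin is contraindicated in patients with a history of severe allergic reactions to cisplatin or other platinum containing compounds".

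Under 5.1.1 every patient receives carboplatin at AUC 5 on day 1 of a 21-day cycle, for six cycles before palbociclib maintenance. Section 5.1 adds: "Protocol treatment must start within 5 business days of enrollment to the study".

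On who checks eligibility, Section 4.0 says: "It is the responsibility of the local site investigator to determine patient eligibility prior to submitting patient registration request to the Coordinating Center". The registrar at the Coordinating Center then reviews the Eligibility Worksheet and the de-identified source documents.

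**The concern.** An eligibility list should stop any patient who cannot be given the mandatory study drug. Here two rules in one protocol disagree, and the looser one controls entry. Section 8.1.2.5 itself treats allergy as a risk of the platinum class: it warns of more allergic reactions, anaphylaxis included, after earlier platinum treatment, and says reactions can begin within minutes.

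Two outcomes are possible for a patient in the gap. If the history is overlooked, the patient receives a drug the protocol says must not be given. If it is noticed after registration but before dosing, the patient has consented, met the mandatory screening biopsy requirement and been registered to no purpose, and is replaced under 5.9.

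**Working it through.** No arithmetic beyond a count applies. The check compares the two rules and then looks for any other criterion that covers the difference.

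**Step 1: compare the two rules.**

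| Drug that caused the severe reaction | Excluded by 3.2.11 and synopsis item 11 | Carboplatin contraindicated by 8.1.1.1 |
|---|---|---|
| Cisplatin | Yes | Yes |
| Carboplatin | Yes | Yes (it is one of the other platinum compounds) |
| Any further platinum compound | No | Yes |

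The contraindication contains the exclusion and goes beyond it. The difference is every platinum compound apart from the two named in 3.2.11.

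**Step 2: look for another criterion that closes the gap.** Section 3 has 9 inclusion criteria (3.1.1 to 3.1.9) and 11 exclusion criteria (3.2.1 to 3.2.11): 9 + 11 = 20. One concerns allergy, which leaves 20 − 1 = 19 to search. The nearest candidates are:

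- **3.2.4** excludes "A serious uncontrolled medical disorder or active infection that would impair their ability to receive study treatment". A past allergic reaction is neither an uncontrolled disorder nor an infection.
- **3.2.1** bars cytotoxic chemotherapy only in the recurrent/metastatic setting, and continues: "Previous treatment with non-cytotoxic agents and/or concurrent chemoradiation in the recurrent/metastatic setting is permitted". It does not reach chemotherapy given earlier, and no criterion excludes a previous different cancer or its treatment. Earlier platinum exposure is therefore compatible with entry.
- **3.1.8** concerns willingness and ability to comply with visits and procedures, not drug tolerance.
- **3.1.9** sets laboratory thresholds.

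None of the 19 mentions platinum or drug hypersensitivity, and none of the 20 refers to Section 8.

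**Step 3: see where a reader would meet the wider rule.** It is stated only in 8.1.1.1. Section 1.3.1 refers the reader to Section 9.0 for carboplatin risks. Section 9.1 describes hypersensitivity but lists no contraindication.

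**Step 4: try to size the gap.** The only allergy figure is 2% hypersensitivity to carboplatin (8.1.4.2, repeated in 9.1). It describes reactions to carboplatin itself, not a history of severe reaction to a different platinum, so it cannot be used here. No other figure is available.

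**Step 5: check the effect on the design.** The two-stage rule in 11.1 (18 then 22 patients, 40 in all, with 9 or more needed to continue and 21 or more to succeed) counts response-evaluable patients. These need at least one dose of each drug. A patient stopped before carboplatin is not counted and is replaced, so the sample size, boundaries, alpha and power do not change.

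**The case against.** The strongest reply is that the protocol already forbids the harm. Section 8.1.1.1 is unqualified and stands under its own heading, and 8.1 also refers to the prescribing information. Medical history is taken at screening, up to 28 days before cycle 1 day 1. The investigator then judges eligibility, and the registrar sees source documents. The limit of 5 business days between enrolment and treatment is therefore not the only time available to notice an allergy. Harm needs a severe platinum reaction to be missed at screening, at registration and at prescribing. All of this stands, and it is why the point is minor.

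A second reply is that the gap is hypothetical, because the documents name no platinum drug beyond cisplatin and carboplatin. This limits what can be said about frequency. It does not remove the conflict, since 8.1.1.1 itself chose the wider wording.

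A third reply is that eligibility lists need not repeat every contraindication. For example, 8.1.1.2 lists significant bleeding, which no Section 3 criterion names. That is fair as a general drafting principle. But here Section 3 does take up the allergy contraindication and states it more narrowly, and nothing in the protocol explains the narrowing. A deliberate choice to admit these patients would contradict 8.1.1.1.

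**Conclusion.** The concern holds as a minor patient-safety correction. Followed as written, Section 3 admits a patient whom 8.1.1.1 bars from the mandatory day-1 drug. The mismatch is certain on the text. How often it would matter is unknown and probably very rare.

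The conclusion rests on a literal reading of 3.2.11 and 3.2.4. An investigator could exclude such a patient on judgement, but no stated criterion requires it. The Eligibility Worksheet is not in the documents, so whether it repeats the narrow wording is also unknown. If it does, the registration check would not ask the question.

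**What to change.** Extend 3.2.11 and synopsis item 11 so that a past severe allergic reaction to cisplatin, carboplatin or any other platinum compound excludes the patient. Make the same change on the Eligibility Worksheet if it carries the narrow wording.

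The cost is a few words in two or three places. The only downside is a rare extra screen failure, of someone who under 8.1.1.1 should not receive carboplatin anyway.
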